CRP/procalcitonin who were treated with steroids or patients with a low CRP/procalcitonin who were not treated with corticosteroids), versus treatment that was biomarker-discordant. The threshold for an elevated CRP was 150mg/L and the threshold for an elevated procalcitonin was 2.2ng/ml. After adjusting for severity of illness, early (within 12 hours of ICU admission) steroid administration in patients with pneumonia or ARDS was associated with decreased persistence or progression of pulmonary and other organ failures, reduced hospital and ICU length of stay and decreased hospital mortality(table 1). Patients with biomarker-concordant and biomarker-discordant corticosteroid treatment had similar baseline severity of illness. Biomarker-concordant corticosteroid treatment was associated with faster recovery of hypoxemia (table 2). No significant differences in mortality or hospital/ICU length of stay were seen between the biomarker-concordant versus the biomarker discordant group.

Table1. Impact of early corticosteroid use on outcomes in ICU patients with pneumonia and ARDS

	Steroids ≤ 12h after ICU admission (N=1047)	Steroids > 12h after ICU admission(N=567)	P value
SOFA Day 1	5 (3-8)	6 (4-8)	0.006
SOFA Day 2	4 (2-6)	5 (3-8)	<0.001
SOFA Day 3	4 (2-7)	5 (3-8)	0.009
PaO ₂ /FiO ₂ at ICU admission	173 (117-250)	161 (108-240)	0.16
PaO ₂ /FiO ₂ after 24h	196 (143-265)	183 (122-255)	0.03
PaO ₂ /FiO ₂ after 48h	209 (145-284)	191 (129-255)	0.03
ICU length of stay	1.98 (1.07-4.0)	3.69 (1.95-7.24)	<0.001
Hospital Length of stay	7.57 (4.55-14.07)	10.4 (6.08-20.8)	<0.001
ICU Mortality	102 (9.7%)	69 (12.2%)	0.15
Hospital Mortality	188 (17.9%)	132 (23.3%)	0.01

Table 2: Impact of steroid use that was concordant versus discordant with markers of inflammation on outcomes in critically ill patients with pneumonia

	Biomarker Concordant (N=130)	Biomarker Discordant(N=114)	P value
FIO ₂ at ICU admission	40 (30, 60)	40 (30, 60)	0.47
FIO ₂ Day 2	35 (28, 50)	40 (31, 50)	0.07
FIO ₂ Day 3	31 (21, 40)	37 (29, 50)	0.004
FIO ₂ Day 4	28.0 (21.0, 37.5)	35 (28, 50)	<.001
FIO ₂ Day 5	28 (21, 36)	28 (24, 45)	0.03
ICU free days (Median estimate (95%CI)	1.97 (-0.50, 4.45)	0.00 (Ref)	0.12
Hospital free days (Median estimate (95%CI)	1.79 (-0.98, 4.57)	0.00 (Ref)	0.21
ICU Mortality (Hazard Ratio with 95% CI)	0.93 (0.31, 2.74)	1.00 (Ref)	0.89
Hospital Mortality (Hazard Ratio with 95% CI)	0.75 (0.36, 1.59)	1.00 (Ref)	0.45
Delirium	36 (27.7%)	34 (29.8%)	0.71

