Hyperglycemia	30 (23.8%)	26 (23.4%)	0.94

[figure not shown]
Team experience: [name] is an Assistant Professor and Senior Associate Consultant in the Division of Pulmonary and Critical Care at the Mayo Clinic. He has expertise in ARDS epidemiology research and the incorporation of biomarkers in ARDS risk prediction. [name] is a clinical fellow in Critical Care at Mayo Clinic, Rochester with an interest in critical care outcomes research. [name] is a research trainee at Mayo Clinic, Rochester also with an interest in critical care outcomes research. [name] is an assistant professor and clinical pharmacist at Mayo Clinic, Rochester with an interest in individualizing pharmacotherapy for critically ill patients with infections. [name] is an internationally renowned leader in ARDS research and founder of our multidisciplinary clinical research laboratory (METRIC), and Director of Critical Care Research at Mayo. Within this group, we have adequate resources, expertise and training to achieve our scientific objectives.

IV. Research Design and Methods

Figure 1 summarizes study design. A two-arm multicenter randomized trial

Hospital presentation:
Emergency Department

Adult Patient with Pneumonia + Acute Hypoxic Respiratory Failure

A. Study Design or Overview

Specific Aims 1 and 3: We plan to perform a two arm multi-center pilot phase II clinical trial. 44 patients with pneumonia (additional strata to include patients with COVID-19 for specific aim 3) and acute respiratory failure defined by $\text{SpO}_2/\text{FiO}_2 < 315$ ($\text{SpO}_2 < 90\%$ on room air or $< 97\%$ on 2L/min O_2) will be included.

- Control arm: Usual care
- Intervention arm: individualized, biomarker concordant steroid use: dosing, titration and duration according to CRP level (Table 3).

Table 3. Biomarker-concordant steroid treatment

CRP (mmol/L)	Methylprednisolone (daily)
<50	None
51 - 100	0.5 mg/kg
101 - 150	0.75 mg/kg
151 - 200	1 mg/kg
>200	1.5 mg/kg

*per ideal body weight

Randomization will be stratified based on the need for high flow nasal cannula oxygen, noninvasive or invasive ventilator support.

Definitions

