- Evolution of respiratory and other organ failures measured by SOFA at time of ICU admission, after 24 hours, after 48 hours and after 72 hours and by the organ failure free days. In the absence of daily arterial blood gas analysis, for respiratory component of SOFA, $\text{PaO}_2/\text{FiO}_2$ ratio will be replaced by $\text{SpO}_2/\text{FiO}_2$ ratio
- Need and duration of vasopressors and inotropes use (based on cardiovascular SOFA sub-score)
- New onset/worsening arrhythmias
- Evidence of myocardial injury determined by daily troponin peak and/or new diagnosis of LV dysfunction ($\text{LVEF} < 40\%$) or new diagnosis of cor pulmonale (\geq moderate RV dysfunction)
- Re-hospitalization for a primary cardiovascular diagnosis within 30 days
- Side effects of steroid (Safety) including
 - Hyperglycemia and its complications- Diabetic ketoacidosis (DKA) and Hyperosmolar hyperglycemic syndrome (HHS), the need for insulin
 - Delirium (measured by CAM-ICU) and
 - New infections in patients with pneumonia and/or ARDS
- Length of ICU and hospital stay
- Time to discontinue oxygen or return to baseline oxygen use
- Requirement and duration of non-invasive and invasive mechanical ventilation
- ICU, and 30, 60 and 90-day mortality
- Discharge, 30, 60, and 90-day disposition (home vs other)

C. Sample Size and Power: In this pilot study, we do not have the power to test the efficacy of the intervention on patient-centered outcomes. However, this pilot data will provide us with potential effect size data necessary for sample size determination for the future phase II/III study.

D. Data Collection: Case Report Forms will be completed by research coordinators and entered in a REDCap database.

E. Data Handling:

- Protected health information will be preserved by having patient data be de-identified and given a study number.
- This data will be recorded using REDCap and JMP. Any written data will be stored in storage files in a locked access building.
- Data will only be accessible to investigators/participating personnel.
- The computers where the data will be stored meet strict security requirements imposed by Mayo Clinic.
- No data containing PHI will be transported on data sticks or laptops without being encrypted or password protected.
- No hardcopy information containing PHI will be transported/removed from the Mayo campus.
- Any hard copies of archival source documentation will be stored in a locked, secure location only accessible to the study personnel.

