- No data will be disclosed to another institution and all identifiers linking to the patient will be destroyed after data collection is complete.

f. Data Analysis

Aims 1 and 3: Continuous outcomes will be compared between treatment arms using linear regression and binary outcomes using chi-square or fishers exact tests. Secondary outcomes will be tested without adjustment for multiple comparisons. Data from this study, including estimated effects of the intervention and sample variation in outcomes, will provide valuable information to plan a well-powered subsequent phase II trial.

Aim 2: The correlation between CRP levels and corticosteroid dosing in those who receive individual-dose steroids versus usual care will be examined using Pearson's correlation coefficient. The effect of CRP levels on the secondary outcomes will be evaluated using multivariable analysis adjusting for severity of illness. The data from this study will help evaluate the usefulness of CRP as a predictive and prognostic enrichment tool and thus help inform and refine the thresholds for initiation, titration and discontinuation of corticosteroids in the subsequent larger study.

Decision to proceed with a larger study: The decision to proceed with a phase II/III study will be based on the following criteria:

- Ability to enroll an adequate number of eligible patients early in the course of illness. The expected hurdles include delayed identification of potentially eligible patients, provider/patient refusal, non-adherence to protocol, and inability to obtain CRP levels in a timely manner.
- Safety; i.e. absence of significant adverse events.

- Preliminary efficacy: ability to show reduction in steroid use, reduced episodes of hyperglycemia and favorable trajectory of pulmonary organ dysfunction.

The data collected will be essential to adequately plan the future study, estimate power and sample size, refine exclusion/inclusion criteria and determine the number and characteristics of future study sites.

g. Feasibility and Time Frame:

We believe that our project is feasible in the time frame of the grant; we hope to use the preliminary data generated from this pilot study to decide about moving forward with a phase II/III study involving a larger study group and more centers (Table 5).

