h. Strengths – This is a well-designed pilot study to examine the feasibility of this approach. Data from this study, including estimated effects of the intervention and sample variation in outcomes, will provide valuable information to plan a well-powered subsequent phase II/III trial.

i. Limitation – Subject enrollment is dependent on availability of research coordinators, therefore we aim to enroll 44 patients within a 2 year period. Randomization by stratification might limit wide generalizability and feasibility if a high proportion of subjects with chronic obstructive lung disease are enrolled. We also acknowledge the fact that the lack of blinding of treating attending physicians and physicians in training is a strong limitation in our study.

V. Human Subjects

Informed consent: All subjects for this study will be provided a consent form describing this study and providing sufficient information for subjects to make an informed decision about their participation in this study. This consent form will be submitted with the protocol for review and approval by the IRB for the study.

The risk profile would justify deferred consent for those who are unable to give consent and have no legally authorized representative available within the short timeframe.

Our inclusion and exclusion criteria have been carefully selected to maximize potential benefit and minimize risk to study subjects.

For suspected/confirmed COVID-19 subjects: Due to the high infectivity of COVID-19, and the strict need to minimize contact between suspected COVID-19 patients and study staff, we propose consent be obtained verbally via telephone or via video.

Patients would still receive a copy of the consent form describing the study. This would be given to the patient by the room nurse to be coordinated with other routine cares.

For all other subjects: The consent form must be signed by the subject or the subject's legally authorized representative, and the individual obtaining the informed consent.

Potential risks: We will include a detailed description of potential risks and benefits of corticosteroid administration while obtaining patient consent.

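### The arm comparison of SOFA at 24, 48 and 72 hours names no covariate, so use of the admission SOFA and the randomisation stratum is left unspecified, and precision may be lost in a 44-patient pilot

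*Combined protocol and SAP*

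**What the plan says.** Section IV.B (Secondary outcomes) lists "Evolution of respiratory and other organ failures measured by SOFA at time of ICU admission, after 24 hours, after 48 hours and after 72 hours", together with organ-failure-free days. Section IV.f (Data Analysis, Aims 1 and 3) gives the method for the arm comparison in one sentence: "Continuous outcomes will be compared between treatment arms using linear regression and binary outcomes using chi-square or fishers exact tests". It names no covariate, change score, repeated-measures model or principal time point for SOFA.

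The only adjustment in the analysis section belongs to Aim 2 and concerns CRP, not the arms: "The effect of CRP levels on the secondary outcomes will be evaluated using multivariable analysis adjusting for severity of illness".

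Section IV.A describes the allocation: "Randomization will be stratified based on the need for high flow nasal cannula oxygen, noninvasive or invasive ventilator support". The analysis section does not mention this factor again.

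The sample size is set by coordinator availability (section IV.i): "we aim to enroll 44 patients within a 2 year period". Section IV.C disclaims power for patient-centred outcomes and says the pilot will supply effect-size data for the next trial.

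**The concern.** The outcome is described as an evolution over four scores, and the first of them is the natural baseline for the other three. The plan collects it but does not say how it is used. Three analyses fit the wording: a raw comparison at each time, a comparison of changes from admission, and a regression on arm and admission score. They differ in precision and can give different estimates from the same data, and nothing fixes the choice before the data are seen.

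In a trial this small, chance differences in admission severity can be comparable in size to plausible effects. A raw comparison carries part of such a difference into the result and leaves explainable variation in the error term. The result is used: estimated effects and sample variation are to inform the next trial's size, and the decision to proceed looks at the course of pulmonary organ dysfunction, to which the respiratory SOFA component is relevant.

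**Working it through.** The plan states no power, alpha, effect size or SOFA variance, so there is no figure to reproduce.

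**Inputs**
- Sample size 44 in two arms (sections IV.A and IV.i). No allocation ratio is stated; 1:1 is assumed, so n = 22 per arm.
- SOFA spread from Table 1. The Day 1 row reads "SOFA Day 1 5 (3-8) 6 (4-8) 0.006". With SD = IQR/1.349, an IQR width of 5 gives 5/1.349 = 3.71 and a width of 4 gives 4/1.349 = 2.97. Of the six SOFA IQRs in Table 1, four have width 5 and two have width 4. The range used is 3.0 to 3.7.
- Correlation rho between baseline and later SOFA: not in the documents. Values of 0.3, 0.5 and 0.7 are assumed.
- Equal SDs over time, complete data and a two-sided 95% interval are also assumed.

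**Chance gap at baseline**

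SD of the gap = SD × sqrt(2/22).
- SD 3.0: 3.0 × 0.3015 = 0.90 points; probability of a gap of at least 1 point, 27%.
- SD 3.7: 3.7 × 0.3015 = 1.12 points; probability of a gap of at least 1 point, 37%.

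**How much carries over**

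With equal SDs the regression slope of later on baseline SOFA is rho, so a 1-point gap shifts the raw later difference by about rho points. In 40,000 simulated trials at SD 3.7 the slope was 0.51 at rho 0.5 and 0.70 at rho 0.7. The mean raw estimate was within 0.01 of zero, which confirms no bias over randomisations. After adjustment the shift at a gap near 1 point was 0.07 or less.

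**Precision**

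Raw half-width = t(42) × SD × sqrt(2/22). At SD 3.7 this is 2.018 × 1.116 = 2.25.

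Adjusted half-width = t(41) × SD × sqrt(2/22) × sqrt[(1 − rho²)(1 + 1/40)], where the last term is the small-sample cost of estimating the slope (2n − 4 = 40). At rho 0.5 this is 2.020 × 1.116 × sqrt(0.75 × 1.025) = 2.020 × 1.116 × 0.877 = 1.98.

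| rho | SE factor, baseline-adjusted | Half-width, SD 3.7 (raw 2.25) | Half-width, SD 3.0 (raw 1.83) | Equivalent raw n per arm, 22/factor² | SE factor, change score, sqrt[2(1 − rho)] |
|---|---|---|---|---|---|
| 0.3 | 0.966 | 2.18 | 1.76 | 24 | 1.18 |
| 0.5 | 0.877 | 1.98 | 1.60 | 29 | 1.00 |
| 0.7 | 0.723 | 1.63 | 1.32 | 42 | 0.77 |

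The standard error falls by about 3%, 12% or 28%. A change score is less precise than the raw comparison when rho is below 0.5, so the readings left open by the plan are not interchangeable. These figures are for one time point with baseline SOFA as the only covariate.

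**The case against.** The strongest reply is that the plan is silent, not expressly unadjusted. Linear regression admits covariates, and words such as evolution and, in Specific Aim 2, trajectories suggest that the first score was meant to be used. This stands. A reader might infer that the sponsor has chosen a raw comparison; the documents do not say so. The defect is an unspecified model.

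A reader might also infer that a chance gap at admission passes in full into the result. It does not: only about rho points per point do, and stratification by respiratory support limits imbalance in that component of SOFA, though not in the total.

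It is tempting to set the 37% chance of a 1-point admission gap against the 1-point Day 3 difference in medians in Table 1 (4 versus 5). These are unlike quantities. To move the later difference by 1 point the baseline gap must be 1/rho, that is 2.0 points at rho 0.5 or 1.43 at rho 0.7. At SD 3.7 the probabilities are about 7% and 20%. Table 1 also compares early with late steroid use in a retrospective cohort whose groups already differed on Day 1 (5 versus 6), so it is no benchmark for this intervention.

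The gain rests on a correlation the documents do not give, and at rho 0.3 it is small. The criterion for proceeding concerns pulmonary dysfunction, whereas the figures above are for total SOFA. Finally, this is a secondary outcome of a pilot whose primary outcome is feasibility. All of this limits the weight of the point. None of it supplies the missing model.

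**Conclusion.** The point holds as a gap in specification with a cheap remedy, not as an error that biases the trial. The planned SOFA comparison does not say that it uses the admission score or the stratification factor. If it is run without them, the estimate remains unbiased over randomisations, but the interval is wider than it need be: at SD 3.7, about 2.25 points against 2.18, 1.98 or 1.63 for rho 0.3, 0.5 or 0.7. A chance baseline gap with an SD of 0.90 to 1.12 points would feed in part into the one result observed. The size depends on 1:1 allocation, SDs read from retrospective IQRs, complete data and an assumed correlation.

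The ICU-admission score is also not guaranteed to be a baseline. Patients are identified in the emergency department, and the inclusion criteria do not require ICU admission. The score may therefore follow randomisation or the first trial dose, or may not exist. Adjusting for a score taken after randomisation could remove part of a treatment effect.

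**What to change.** In section IV.f, add for SOFA: one mixed model for the 24, 48 and 72 hour scores, with arm, time, arm-by-time, baseline SOFA and the respiratory-support stratum as covariates, reporting the adjusted 72 hour difference with its 95% CI.

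Define baseline as the last SOFA that can be computed from routine records at or before randomisation, and state that no score taken after randomisation will be substituted. A score taken after a steroid dose from the primary service is still a valid baseline if it precedes randomisation.

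Apply the same adjustment to the respiratory SOFA component, which is closer to the pulmonary criterion for proceeding than the total score is.

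The cost is a short addition to the analysis section, a few degrees of freedom, and some chart abstraction where the ICU-admission score follows randomisation or the patient never enters the ICU. No extra patients or visits are needed.

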This pilot study is being conducted to assess the feasibility of recruiting patients and clinician adherence to steroid protocol, to refine the trial intervention and endpoints, and to calculate target sample sizes in preparation for a larger pragmatic clinical trial comparing the two approaches to corticosteroid administration.

Specific Aim 2: To evaluate the trajectories of C-reactive protein (CRP), pulmonary and non-pulmonary organ failures over time in patients from the two study arms.

In addition to assessing the feasibility of individualized, biomarker guided steroid dosing, this pilot study is necessary to evaluate the usefulness of CRP as a predictive enrichment tool in identifying patients in whom steroid administration will be most beneficial and also as a prognostic enrichment tool (alongside severity of pulmonary and other organ failures) to identify patients at higher risk of poor outcomes. It will inform the target population and will help refine the thresholds for initiation, titration and discontinuation of individualized corticosteroid therapy used to reduce inflammation in patients with pneumonia and acute hypoxic respiratory failure

Specific Aim 3: To evaluate the role of a biomarker-titrated adjuvant corticosteroid administration compared to usual care in patients admitted to hospital with SARS Co-V 2 (COVID-19) infection. We hypothesize that, compared to usual care, individualized biomarker-titrated dosing will be associated with:

- a) Improvement in pulmonary organ function based on requirements for oxygen and advanced respiratory support

- b) Reduced hospital length of stay
- c) Reduced cardiovascular complications including evidence of myocardial injury, need for inotropes and new/worsening arrhythmias

II. Background and Significance

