In the individualized, biomarker-concordant arm, all patients will receive steroids once at the time of admission, then a daily morning dose. In order to account for varying turnaround time at different laboratories, CRP levels will be drawn with early morning labs, and used to determine the steroid dosing for the day. Patients will receive daily CRP measurements for the first 5 days of the hospitalization, or until hospital discharge. Steroid administration will be facilitated using standardized computerized physician order entry. Steroid order sets will include 6 hourly point of care glucose monitoring, and an insulin sliding scale for glucose levels to facilitate glucose management. The need for insulin drip will be determined by the treating physician. Additional testing including serum and urine ketones will be informed by the glucose level, serum anion gap and bicarbonate levels in routine basic metabolic panels and determined by the treating physician. Glucose levels, new or worsening infections within 30 days of start of steroid (positive blood/sputum/urine culture) and Confusion Assessment Method in the ICU will be documented in case report forms.

In the usual care arm, patients will receive daily CRP measurements for the first 5 days of the hospitalization, or until hospital discharge. However, these CRP measurements will not be accessible to the treating physicians.

An oxygen titration protocol will be utilized to standardize oxygen weaning in both arms (please see appendix).

Daily Troponin measurements will be added in both arms

Primary outcomes:

- Feasibility: a percentage of eligible patients adhered to the timely initiation and daily treatment according to ESICM/SCCM clinical practice guideline (control group) or biomarker concordance (intervention group)

Secondary outcomes

- Death
- Progression of disease as defined by the need for high flow nasal cannula oxygen, noninvasive or invasive ventilation. Given the proliferation of high flow nasal cannula oxygen use in lieu of mechanical ventilation, instead of ventilator-free days we opt for

using advanced respiratory support free days where “advanced respiratory support” includes both invasive and noninvasive mechanical ventilation and the high flow nasal cannula oxygen.

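### In the intervention arm the planned CRP-dose correlation is largely fixed by Table 3 and the CRP spread, so it cannot inform the dosing thresholds, and no planned analysis compares cut-points

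*Combined protocol and SAP*

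**What the plan says.** Section IV.A (Study Design or Overview) defines the intervention as "dosing, titration and duration according to CRP level (Table 3)". Table 3 gives five CRP tiers with one daily methylprednisolone dose each: none, 0.5, 0.75, 1 and 1.5 mg/kg, "per ideal body weight". Section IV.B (Protocol) makes the link a same-day one: "CRP levels will be drawn with early morning labs, and used to determine the steroid dosing for the day". In usual care, dosing is left to the treating team and the study's CRP values are hidden from it.

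Section IV.f (Data Analysis), Aim 2, plans two analyses. The first reads: "The correlation between CRP levels and corticosteroid dosing in those who receive individual-dose steroids versus usual care will be examined using Pearson's correlation coefficient." The second relates CRP to the secondary outcomes in a severity-adjusted multivariable model. The paragraph closes by saying that the data will "help inform and refine the thresholds for initiation, titration and discontinuation of corticosteroids in the subsequent larger study". Specific Aim 2 in section I makes the same promise: the study "will help refine the thresholds for initiation, titration and discontinuation of individualized corticosteroid therapy".

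Delivery has its own measure. The primary feasibility outcome in section IV.B is the percentage of eligible patients who adhered to their arm's regimen.

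**The concern.** A correlation is informative when two quantities are free to vary separately. In the intervention arm they are not: a protocol table converts CRP into dose. A high r there shows mainly that the table rises with CRP. A lower r may mean off-table dosing, or only that many patients sat above 200 mg/L, where the dose no longer changes.

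The threshold promise adds to the concern. To choose among cut-points one needs outcomes, and different doses at the same CRP. The intervention-arm r contains neither. Each tier has one assigned dose, so the arm has no planned dose contrast within a tier, and across tiers dose and CRP move together. At stake is what the pilot can hand to the larger trial: a statement about thresholds that none of its planned analyses can support.

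**Working it through.** **Inputs.** The doses and cut-points are those of Table 3. The plan gives no expected r, target or CRP distribution, so there is no figure of its own to reproduce. It also does not state the unit of analysis (patient or patient-day) or the dose scale (mg or mg/kg). Assumptions here: CRP uniform on 0-300 mg/L, dose in mg/kg, and values from 50 up to 51, which Table 3 leaves unassigned, placed in the lowest tier.

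**Perfect delivery.** The tier shares are 1/6, 1/6, 1/6, 1/6 and 1/3.

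- Mean dose: (0 + 0.5 + 0.75 + 1)/6 + 1.5/3 = 0.875
- Mean squared dose: (0 + 0.25 + 0.5625 + 1)/6 + 2.25/3 = 1.0521
- SD of dose: √(1.0521 − 0.875²) = √0.2865 = 0.5352
- Mean of CRP × dose, using tier midpoints: (25×0 + 75×0.5 + 125×0.75 + 175×1)/6 + (250×1.5)/3 = 51.04 + 125 = 176.04
- Covariance: 176.04 − 150 × 0.875 = 44.79
- SD of CRP: 300/√12 = 86.60
- r = 44.79/(86.60 × 0.5352) = **0.966**

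**Delivery errors.** Halving every dose halves both the covariance and the dose SD, so r does not move. If a fraction q of doses is omitted at random, r = (1−q) × 44.79 / {86.60 × √[(1−q) × 1.0521 − (1−q)² × 0.7656]}. For q = 0.1 this is 40.31/(86.60 × 0.5716) = 0.814. The same method gives the other rows. They illustrate errors and are not proposed regimens.

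| Delivery | Patient-days off the Table 3 dose | r |
|---|---|---|
| Perfect | 0% | 0.966 |
| Every dose halved | 5/6 = 83% | 0.966 |
| Every dose one tier low | 5/6 = 83% | 0.948 |
| Every dose one tier high | 4/6 = 67% | 0.928 |
| 10% omitted at random | 0.1 × 5/6 = 8% | 0.814 |
| 30% omitted at random | 0.3 × 5/6 = 25% | 0.602 |

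So r responds to random errors but not to uniform scaling, and it ranks these cases differently from the share of days off the table.

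**Cut-points.** Raising all four cut-points by 25 gives r = 0.974; raising them by 50 gives 0.966. No outcome enters the formula, so neither value favours either table.

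**CRP spread, perfect delivery throughout.** r is 0.920 for CRP uniform on 0-400, 0.947 for a normal distribution with mean 150 and SD 80, and 0.76 to 0.80 for three lognormal distributions. It is undefined if every value exceeds 200. On the mg scale, with ideal weight assumed to be 64 kg (SD 10), the first case falls from 0.966 to 0.927.

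**At pilot size.** I simulated 22 patients over 5 days (1:1 allocation assumed), with lognormal first-day CRP, median 60 to 250 mg/L, log-SD 0.5 to 0.9, and a decline of 0 to 40% per day. The median r runs from about 0.6 to 0.94 with perfect delivery, and from about 0.4 to 0.7 with 20% of days dosed at a random tier. With log-SD 0.7 and no decline, perfect delivery at median CRP 250 gives 0.64, while 20% random tiers at median CRP 100 gives 0.70.

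**The second Aim 2 analysis.** In the intervention arm, at r = 0.966, only 1 − 0.966² = 0.07 of the dose variance is not linearly explained by CRP. Where r is lower under perfect delivery, the remainder is still the steps and ceiling of the table, not independent variation in dose. A CRP-outcome model cannot separate CRP from assigned dose in that arm except through the functional form chosen. Dose can differ at the same CRP between the randomized arms, but the plan states no arm-by-CRP term to use that contrast.

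**The case against.** The best defence is that the plan asks less of r than a critic might suppose. A reader might infer three stronger points, and the documents support none of them.

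- *That the threshold promise rests on r alone.* It does not. Section IV.f credits the promise to the study data as a whole, and the severity-adjusted CRP-outcome model stands between the correlation and the promise.
- *That r is the trial's measure of delivery, or is blind to delivery.* Adherence is the primary outcome, and the plan never gives that task to r. Nor is r blind: when simulated pilots share one CRP distribution, perfect delivery gave a higher r than 20% random dosing in 82% to 100% of comparisons. The 0.64 versus 0.70 reversal arises only across different CRP distributions.
- *That cut-points would be changed because of r.* No passage says so, and r is not among the criteria for proceeding to a larger study.

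The usual-care half of the comparison is also sound. Dosing there is discretionary and the study's CRP values are hidden, so the association can show whether ordinary dosing tracks inflammation and how far the arms separate. The wording on thresholds is modest, in a pilot that declares itself unpowered for efficacy on patient-centred outcomes.

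All of this stands, and it limits the point. It does not give the intervention-arm r a use for thresholds, and it does not supply an analysis that compares cut-points.

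**Conclusion.** The concern holds in a limited form. In the intervention arm the planned correlation is largely a product of Table 3 and the enrolled patients' CRP spread. It cannot inform the thresholds for starting, adjusting or stopping steroids, and it is not a valid stand-alone check on delivery. The CRP-outcome model does not close the gap as written.

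The built-in dependence, the absence of any outcome, and the invariance to halved doses follow from Table 3 and the definition of r, without any assumption about CRP. The numerical values of r do rest on assumed CRP distributions and are illustrative. About 22/5 = 4.4 intervention patients would fall in each tier, but only with 1:1 allocation, which is not stated, and an even spread. No primary outcome or go/no-go criterion depends on r, so the consequence is confined to what Aim 2 can claim.

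**What to change.** 1. In the intervention arm, replace Pearson's r with the percentage of patient-days on the Table 3 dose and the mean given-minus-assigned difference in mg/kg. This complements the primary adherence outcome at the patient-day level. State how the admission dose is handled: section IV.B says "all patients will receive steroids once at the time of admission, then a daily morning dose" without tying that first dose to a tier, and Table 3 has a row with no steroid. The two passages must be reconciled before agreement can be scored, as must the gap between 50 and 51.
2. Keep the CRP-dose association for usual care, stating the unit of analysis and dose scale, with an interval. With 22 independent observations the 95% interval around r = 0 is −0.42 to 0.42 (tanh of ±1.96/√19).
3. Tabulate both randomized arms by first-CRP tier: patients, dose given, tier changes, outcomes. Include arm and an exploratory arm-by-CRP term in the CRP-outcome model.
4. In Specific Aim 2 and section IV.f, restate the claim as describing tier occupancy and between-arm dose contrast, not refining cut-points.

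The cost is wording. Daily CRP is already planned in both arms, and dose data are needed for the cumulative-exposure hypothesis in Aim 1. The price is a more modest stated aim and exploratory estimates that will be imprecise at 44 patients.
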